Investigational product, dosage and mode of administration:

CTP-543 will be dosed orally as tablets at doses of 8 mg BID, every 12 hours or 16 mg QD in the morning with matching placebo in the evening.

Reference therapy, dosage and mode of administration:

N/A

Duration of treatment:

Patients will receive up to 24 weeks of study drug

Duration of study participation:

Patients will participate in the study for up to approximately 32 weeks if exiting the study after the 4 week Safety Follow-up (4-week Screening, 24-week Treatment, 4 week Safety Follow-up). Upon completion of the 24-week Treatment Period, patients will be eligible to either complete treatment and exit the study following the 4-week Safety Follow-up visit, or roll-over into a long-term open-label extension study.

Criteria for evaluation:

Efficacy:

The primary efficacy endpoint will be the relative change in SALT score for each dose regimen from baseline at Week 24.

Secondary efficacy endpoints in each dose regimen include:

- Proportion of patients achieving at least a 90%, 75%, and 50% reduction in SALT score from baseline at Weeks:
 - 4, 8, 12, 16, 20, and 24 in the Treatment Period
- Absolute change in SALT scores from baseline at Weeks:
 - 4, 8, 12, 16, 20, and 24 in the Treatment Period
- Relative change in SALT scores from baseline at Weeks:
 - 4, 8, 12, 16, 20 and 24 in the Treatment Period
- Change in satisfaction of hair coverage as reported by patient

Exploratory Endpoints in each dose regimen include:

- Change in patient's eyebrows as measured by the patient's Visual Analog Scale (VAS)
- Change in satisfaction of hair coverage quality as reported by patient

Safety:

Tolerability of CTP-543 will be assessed by evaluating adverse events, vital signs, concomitant medications, clinical laboratory and electrocardiogram results, as well as physical examinations.

Statistical methods:

Sample Size:

A sample size of 25 patients (completers) per group provides adequate precision for the estimated dosing regimen difference for relative change in SALT score from baseline at Week 24. Precision of the estimated difference is quantified by the width of the 90% confidence interval for the dosing regimen difference.

Efficacy Analyses:

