Concomitant medications ¹³	X	X	X	X	X	X	X	X

HBV= hepatitis B virus; HCV = hepatitis C virus

¹ Randomization/Day 1 may occur any time after Screening laboratory results are available and reviewed by the Investigator.

² All subsequent visits and week increments should be based on the date of Visit 2. All visit windows are ± 3 days.

³ Also serves as the Early Termination Visit for patient withdrawal in this period.

⁴ The Safety Follow-Up Visit is intended for those patients who do not roll over into an open-label extension and for patients who have been discontinued from the study and completed the Early Termination Visit (Week 24).

⁵ Serum pregnancy test for females of childbearing potential only.

⁶ Urine pregnancy test should be performed at the randomization visit.

⁷ Includes hematology and serum chemistry.

⁸ Collected pre-dose, except on Visit 11.

⁹ Will include thyroid stimulating hormone and hemoglobin A1c at Screening only.

¹⁰Includes total cholesterol, low-density lipoprotein, high-density lipoprotein, and triglycerides.

¹¹ Should be performed by the same rater for the patient for the duration of the study.

¹²Sites will take photographs of patient's scalps and eyebrow/eyelashes, if involved, to provide visual support of baseline SALT as well as potential SALT changes throughout the study.

¹³Collection is ongoing.

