10. ADVERSE EVENTS

10.1. Definition of Adverse Event

An adverse event is any untoward medical occurrence that may appear or worsen in a patient during the course of a study. It may be a new intercurrent illness, a worsening concomitant illness, an injury, or any concomitant impairment of the patient's health, including laboratory test values, regardless of etiology. Any worsening (ie, any clinically significant adverse change in the frequency or intensity of a pre-existing condition) should be considered an adverse event. A diagnosis or syndrome should be recorded on the adverse event page of the eCRF rather than the individual signs or symptoms of the diagnosis or syndrome. A worsening of the condition under study, alopecia areata, will not be reported as an adverse event.

All patients will be monitored for adverse events during the study. Assessments may include monitoring of the following parameters: the patient's clinical symptoms, laboratory, physical examination findings, or findings from other tests and/or procedures.

An adverse event reported after informed consent, but before the first dose of study drug (i.e., Day 1), will be considered a pretreatment adverse event and will be captured on the eCRF. Adverse events will be considered treatment-emergent if the onset is after the first dose of study drug or if an ongoing Adverse Event worsens after dosing is initiated.

An abnormal laboratory value is considered to be an adverse event if the abnormality:

- results in discontinuation from the study;
- is judged by the Investigator to be of significant clinical importance requiring treatment, modification/interruption of investigational product dose, or any other therapeutic intervention

Regardless of severity grade, only laboratory abnormalities that fulfill a seriousness criterion need to be documented as a serious adverse event.

If a laboratory abnormality is one component of a diagnosis or syndrome, then only the diagnosis or syndrome should be recorded on the adverse event eCRF. If the abnormality was not a part of a diagnosis or syndrome, then the laboratory abnormality should be recorded as the adverse event. If possible, the laboratory abnormality should be recorded as a medical term and not simply as an abnormal laboratory result (e.g., record thrombocytopenia rather than decreased platelets).

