11.4.4. Safety

All safety summaries will be descriptive with no statistical hypothesis testing and based on the Safety Population. All safety endpoints will be listed in by-patient data listings.

Adverse events will be coded using MedDRA and summarized by system organ class and preferred term. Clinically significant deteriorations in physical examination findings will be reported and summarized as adverse events.

Laboratory values will be converted to the project-defined unit of measurement, as applicable, before analysis. Abnormal, clinically significant laboratory values will be reported and summarized as adverse events.

Adverse Events

An adverse event reported after informed consent, but before the first dose of study drug (i.e., Day 1), will be considered a pre-treatment adverse event. Treatment-emergent adverse events (TEAEs) will be defined as any adverse event that occurs after administration of the first dose of

study drug until Week 24 or the Early Termination Visit. The number and percentage of patients who report TEAEs will be summarized by system organ class and preferred term.

Treatment emergent adverse events will also be summarized by intensity as well as relationship to study drug.

Patients who report the same preferred term on multiple occasions will be counted once for the preferred term: under the highest severity when summarized by severity and under the closest relationship to study drug when summarized by relationship. If a patient reports multiple preferred terms for a system organ class, the patient will be counted only once for that system organ class.

The number and percentage of patients who experience TEAEs will be summarized by dosing regimen for the following:

- By system organ class and preferred term
- By severity/intensity, system organ class, and preferred term
- By relationship to study drug, system organ class, and preferred term
- Serious adverse events by system organ class and preferred term
- Serious adverse events by relationship to study drug, system organ class, and preferred term
- Adverse events resulting in discontinuation of study drug by system organ class and preferred term
- Adverse events that result in study drug dose interruption by system organ class and preferred term

By-patient listings will be provided for any deaths, serious adverse events, and adverse events leading to discontinuation of treatment.

Clinical Laboratory

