### **9.2 Adverse Events**

Adverse events will be coded using MedDRA and summarized by system organ class and preferred term. Clinically significant deteriorations in physical examination findings will be reported and summarized as adverse events.

An adverse event reported after informed consent, but before the first dose of study drug (i.e., Day 1), will be considered a pre-treatment adverse event. Treatment-emergent adverse events will be defined as any adverse event that occurs after administration of the first dose of study drug. The number and percentage of patients who report TEAEs will be summarized by system organ class and preferred term.

Treatment emergent adverse events will also be summarized by intensity as well as relationship to study drug.

Partial dates will be imputed for the purposes of defining TEAEs as follows:

- For a missing start day where the month and year are present, the start day will be set to the first day of the month, unless 1) the first day of the month is before the date of administration of study drug and the month and year are the same as the month and year of the date of administration of study drug, and 2) the end date is on or after the date of

administration of study drug or the end date is completely missing, in which case the start day will be set to the first day of administration of study drug.

- For a missing start day and month where the year is present, the start day and month will be set to January 1st, unless 1) January 1st is before the date of administration of study drug, and 2) the end date is on or after the date of administration of study drug or the end date is completely missing, in which case the start day and month will be set to that of the first date of administration of study drug.
- For a missing end day where the month and year are present, the end day will be set to the last day of the month, unless the month and year are the same as the month and year of the last contact date for the patient, in which case the end day will be set to that of the patient's last contact date.
- For a missing end day and month where the year is present, the end day and month will be set to the patient's last contact date, unless the year of the patient's last contact date is greater than the end year, in which case the end day and month will be set to December 31st.

For an entirely missing stop date (i.e. day, month, and year are missing), the TEAE will be treated as ongoing.

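### SAP 9.2 drops the protocol's end to the TEAE window without recording the change, so off-drug Week 24 to 28 events can count only for patients who do not roll over; the protocol's worsening rule is also unstated

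*SAP*

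**What the plan says.** Treatment-emergence is defined in three places.

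- **SAP 9.2:** "Treatment-emergent adverse events will be defined as any adverse event that occurs after administration of the first dose of study drug". There is no end date and no mention of worsening. The same section says that an event reported after consent but "before the first dose of study drug (i.e., Day 1), will be considered a pre-treatment adverse event".
- **Protocol 11.4.4:** events after the first dose of "study drug until Week 24 or the Early Termination Visit". There is an end date but no mention of worsening.
- **Protocol 10.1:** an event is treatment-emergent "if the onset is after the first dose of study drug or if an ongoing Adverse Event worsens after dosing is initiated". Worsening is included and there is no end date. The same section also says: "Any worsening (ie, any clinically significant adverse change in the frequency or intensity of a pre-existing condition) should be considered an adverse event".

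On timing, the Protocol synopsis says: "Patients will receive up to 24 weeks of study drug". A 4-week safety follow-up comes after that. Footnote 4 to Protocol Table 1 says: "The Safety Follow-Up Visit is intended for those patients who do not roll over into an open-label extension". The footnote also covers discontinued patients who have had the Early Termination Visit. SAP 8.4.3 treats the Week 28 visit and entry to the extension as alternatives.

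SAP Section 1 undertakes to document changes from the protocol's analyses. SAP Section 12 lists one change, the added SALT threshold analyses.

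**The concern.** Comparing the tolerability of the two regimens is part of the study's overall objective, and the TEAE flag feeds ten planned tables (14.3.1.1 to 14.3.1.10). These are crude counts and percentages of patients. SAP Section 3 sets the denominator at the population header count, and no exposure-adjusted rate is planned. A difference in how long patients are observed therefore passes straight into the percentages.

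Without an end date, how long a patient is observed for TEAEs depends partly on whether that patient enters the extension. That decision is made after treatment and could differ by regimen. The events added in this way arise off drug.

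The silence on worsening is a separate gap. A pre-dose condition that deteriorates on treatment is treatment-emergent under Protocol 10.1. Under SAP 9.2 its status depends on how the site enters it.

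**Working it through.** **No figure to reproduce.** The documents give no expected TEAE rate and no roll-over share. The check compares the texts and then sizes the effect on stated assumptions.

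**1. Definitions side by side**

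| Source | End of window | Worsening of an ongoing event |
|---|---|---|
| Protocol 10.1 | none stated | counted |
| Protocol 11.4.4 | Week 24 or Early Termination Visit | not mentioned |
| SAP 9.2 | none stated | not mentioned |

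On the window, Protocol 11.4.4 stands against the other two. On worsening, Protocol 10.1 stands against the other two.

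**2. Do Week 24 to 28 events reach the data?** Yes. The Schedule of Events marks adverse event collection at Week 28, and Protocol 10.5 requires recording through the final study visit. A roll-over's last visit in this study is Week 24. Serious events are separately reportable to 30 days after the last dose (Protocol 10.6); the documents do not say whether one arising in the extension would also be entered here.

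**3. Extra observation.** For a completer who does not roll over, the treatment window is 24 × 7 = 168 days and the follow-up is 4 × 7 = 28 days. 28/168 = 16.7%. For early terminators the figure varies:
- their treatment window is shorter than 168 days;
- Protocol 7.3.1 lets the sponsor waive the follow-up visit for some who stopped dosing before the Early Termination Visit;
- Protocol 10.6 can be read as ending non-serious reporting at early termination, whereas Protocol 10.5 and the schedule run to the final visit.

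**4. Effect on the percentages (illustration).** Assume a constant hazard, the same off drug as on drug, and roll-over unrelated to event risk. Let p be the 24-week incidence and r the share rolling over.

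- 28-week incidence: q = 1 − (1 − p)^(28/24)
- Arm percentage under SAP 9.2: p + (1 − r)(q − p)
- Artificial arm difference with equal p: (difference in r) × (q − p)
- For scale, the 90% half-width for a difference with 30 per arm: 1.645 × √(2p(1 − p)/30)

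Example with p = 40%: q = 1 − 0.60^(28/24) = 44.90%, so q − p = 4.90 points. A 30-point roll-over difference gives 0.30 × 4.90 = 1.47 points.

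| p (%) | q (%) | q − p (points) | Artefact, 30-point roll-over gap (points) | 90% half-width (points) |
|---|---|---|---|---|
| 5 | 5.81 | 0.81 | 0.24 | 9.3 |
| 10 | 11.57 | 1.57 | 0.47 | 12.7 |
| 20 | 22.92 | 2.92 | 0.88 | 17.0 |
| 40 | 44.90 | 4.90 | 1.47 | 20.8 |
| 60 | 65.67 | 5.67 | 1.70 | 20.8 |
| 80 | 84.71 | 4.71 | 1.41 | 17.0 |

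The q − p column is also the extreme case, with everyone rolling over in one arm and nobody in the other.

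**5. Worsening.** If a post-dose worsening is entered as a new event, it occurs after the first dose and SAP 9.2 captures it. If it stays on the record opened before the first dose, SAP 9.2 classes it as pre-treatment. Each patient affected moves an arm's percentage by 1/30 = 3.3 points. The documents do not indicate how many there would be.

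**The case against.** A reader might infer that three incompatible definitions would necessarily give different adverse event rates. The texts do not support that. Counts differ only if an event starts after Week 24 or the Early Termination Visit, or if a pre-dose event worsens without a new record. Nor do the documents show that worsening is excluded, because Protocol 10.1 makes any clinically significant worsening an adverse event in its own right. What stands is that the result depends on data entry, which neither document settles.

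A reader might also infer that the regimen comparison is biased. That requires roll-over or discontinuation to differ by arm. Both arms receive active drug at the same total daily dose, patients and sites are unaware of regimen, and no roll-over figure is given. With similar roll-over, both arms rise by about the same amount.

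The consequences are limited in any case. Safety summaries are descriptive, all adverse events are listed by patient (Listing 16.2.7.1), and the SALT endpoints are untouched. The table shells are not available here and may state a window. These points hold and are why the matter is minor. They do not remove the contradiction between SAP 9.2 and Protocol 11.4.4, or its absence from SAP Section 12.

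Finally, closing the window at the Early Termination Visit does not equalise observation for patients who stop early, and the closed window can still contain off-drug days when dosing ends before that visit. This is a fair limit on the remedy.

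**Conclusion.** The point holds as a minor specification fault. SAP 9.2 removes an end date that Protocol 11.4.4 sets, and SAP Section 12 does not record it. As written, off-drug events between Week 24 and Week 28 can count for patients who do not roll over and not for roll-overs.

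The extra observation is up to 16.7%, for completers who do not roll over only. On the assumptions above, a 30-point roll-over difference would create an arm difference of about 0.2 to 1.7 points, and the extreme case 0.8 to 5.7 points. Both are small beside a 90% half-width of about 9 to 21 points. The incidences, the roll-over gap and the constant hazard are assumptions, not figures from the documents.

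The worsening gap is real but conditional: it affects only worsenings left on a pre-dose record.

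**What to change.** - In SAP 9.2, use one definition for the by-regimen TEAE tables: onset or worsening after the first dose, through Week 24 or the Early Termination Visit. This combines Protocol 10.1 and 11.4.4.
- State how a worsening is recognised in the data, whether as a new record or by a rule applied to the existing one.
- Tabulate events after the window separately, as follow-up events, so that nothing is discarded.
- Align Protocol 10.1 and 11.4.4 with that definition, and record any remaining difference in SAP Section 12.

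The cost is a few sentences of SAP text, one flag in the adverse event dataset, one short table and the protocol wording. The window change needs no new data. It removes the dependence on roll-over; the report should say that early terminators still have shorter observation.

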### **9.3 Clinical Laboratory Evaluation**

Observed measurements along with change from baseline for each assessment will be summarized descriptively by dosing regimen and visit for each clinical laboratory parameter.

Hematology parameters for patients that meet Grade 3 or Grade 4 toxicity criteria from the CTCAE v4.0 will be summarized for each scheduled visit and overall for all post-baseline visits. In addition, hematology parameters of interest will be plotted as mean values over time. Serum chemistry parameters for patients that meet Grade 3 or Grade 4 toxicity criteria from the CTCAE v4.0 will be summarized for each scheduled visit and overall for all post-baseline visits.

Laboratory values will be converted to International System of Units (SI) before analysis. If laboratory values are recorded as above or below a threshold (i.e. “<2”, “>30”, etc.), they will be counted as missing for continuous summaries. Abnormal, clinically significant laboratory values (per Investigator judgment) will be reported and summarized as AEs.

All laboratory parameter results will be included in by-patient data listings. Reference ranges for each clinical laboratory parameter will also be summarized in a data listing.

## **9.4 Vital Signs, Physical Findings, and Other Observations Related to Safety**

### **9.4.1 Vital Signs**

Baseline will be defined as the last vital sign value obtained before the first dose of study drug on Day 1; if Day 1 values are unavailable, then values obtained at the Screening Visit will be used. Observed vital sign measurements along with change from baseline for each assessment will be summarized descriptively by dosing regimen and visit for each vital sign variable specified in the protocol (Systolic Blood Pressure, Diastolic Blood Pressure, Pulse Rate, Respiratory Rate, and Oral Temperature). Vital signs will also be presented for each patient in a data listing.

### **9.4.2 ECG**

Observed Overall ECG Interpretations will be summarized as Normal, Abnormal and Not Clinically Significant, or Abnormal and Clinically Significant for each scheduled visit by dosing regimen. In addition, observed and change from baseline measurements of ECG intervals (PR, QT, QTcF, QRS, and RR) for each scheduled assessment will be summarized descriptively by dosing regimen and visit as well as listed within a by-patient data listing. Patients receiving study drug will be identified and summarized by dosing regimen and visit, as well as overall for the following clinically notable categories:

- QTcF > baseline and > 450 msec
- QTcF > baseline and > 480 msec
- QTcF > baseline and > 500 msec
- QTcF increase from baseline > 30 msec
- QTcF increase from baseline > 60 msec

#### **9.4.3 Physical Examinations**

A listing of physical examinations will be provided. Deteriorations from baseline on physical examination will be coded as adverse events and summarized as such.

## **10. PHARMACOKINETIC EVALUATION**

Pharmacokinetic endpoints will not be collected for this study.

## **11. INTERIM ANALYSES AND DATA MONITORING**

No interim analyses or data monitoring committee are planned for this study.

## **12. CHANGES TO THE ANALYSES PLANNED IN THE PROTOCOL**

The following alterations were made to the original analyses planned in the protocol:

- Additional analyses of patients who achieve absolute SALT scores of  $\leq 10$ ,  $\leq 20$ , or  $\leq 25$  at Weeks 4, 8, 12, 16, 20, and 24 were added.

## 14. LIST OF PLANNED TABLES

Table ID	Table No.	Title	Population	Unique?
DS_TAA	14.1.1	Summary of Patient Disposition	All Screened Patients	Y
DS_TAB	14.1.2	Summary of Protocol Deviations	All Randomized Patients	Y
DM_TAA	14.1.3	Summary of Demographics	All Randomized Patients	Y
DM_TAB	14.1.4	Summary of Baseline Characteristics	All Randomized Patients	Y
MH_TAA	14.1.5	Summary of Medical History by System Organ Class and Preferred Term	Safety Population	Y
EX_TAA	14.1.6	Summary of Study Drug Administration and Compliance by Dosing Regimen	Safety Population	Y
CM_TAA	14.1.7.1	Summary of Prior Medications	Safety Population	Y
CM_TAB	14.1.7.2	Summary of Concomitant Medications	Safety Population	N
EF_TAA	14.2.1	Summary of Relative Change from Baseline in Total SALT Score at Week 24	Efficacy Population	Y
EF_TAC	14.2.2.1	Summary of Total SALT Scores by Dosing Regimen and Visit	Efficacy Population	Y
EF_TAE	14.2.2.2	Summary of 90%, 75%, and 50% Responders (SALT Relative Change) by Visit	Efficacy Population	Y
EF_TAG	14.2.2.3	Summary of Satisfaction of Hair Coverage Question	Efficacy Population	Y
EF_TAH	14.2.2.4	Shift from Baseline to Week 24 Satisfaction of Hair Coverage Question	Efficacy Population	Y
EF_TAI	14.2.3.1	Summary of Visual Analog Scale for Eyebrows (mm)	Efficacy Population	Y
EF_TAJ	14.2.3.2	Summary of Satisfaction of Hair Coverage Quality Questions	Efficacy Population	N
EF_TAK	14.2.3.3	Shift from Baseline to Week 24 Satisfaction of Hair Coverage Quality Questions	Efficacy Population	N

EF_TAL	14.2.3.4	Analysis of Patients Achieving $\leq 10$ , $\leq 20$ , or $\leq 25$ Absolute SALT Scores by Visit	Efficacy Population	Y
AE_TAA	14.3.1.1	Summary of Treatment-Emergent Adverse Events	Safety Population	Y
AE_TAB	14.3.1.2	Summary of Treatment-Emergent Adverse Events by System Organ Class and Preferred Term	Safety Population	Y
AE_TAC	14.3.1.3	Summary of Treatment-Emergent Serious Adverse Events by System Organ Class and Preferred Term	Safety Population	N
AE_TAD	14.3.1.4	Summary of All Treatment-Emergent Adverse Events Leading to Discontinuation of Study Drug System Organ Class and Preferred Term	Safety Population	N
AE_TAE	14.3.1.5	Summary of Treatment-Emergent Adverse Events Resulting in Study Dose Interruption by System Organ Class and Preferred Term	Safety Population	N
AE_TAF	14.3.1.6	Summary of CTCAE Grade 3-4 Hematology Treatment-Emergent Adverse Events by System Organ Class and Preferred Term	Safety Population	N
AE_TAG	14.3.1.7	Summary of CTCAE Grade 3-4 Serum Chemistry Treatment-Emergent Adverse Events by System Organ Class and Preferred Term	Safety Population	N
AE_TAH	14.3.1.8	Summary of Treatment-Emergent Adverse Events by Severity/Intensity, System Organ Class, and Preferred Term	Safety Population	Y
AE_TAI	14.3.1.9	Summary of Treatment-Emergent Adverse Events by Relationship to Study Drug, System Organ Class, and Preferred Term	Safety Population	N
AE_TAJ	14.3.1.10	Summary of Treatment-Emergent Serious Adverse Events by Relationship to	Safety Population	N

		Study Drug, System Organ Class, and Preferred Term		
LB_TAA	14.3.4.1.1	Summary of All Clinical Laboratory Values: Hematology	Safety Population	Y
LB_TAB	14.3.4.1.2	Summary of All Clinical Laboratory Values: Serum Chemistry	Safety Population	N
LB_TAC	14.3.4.2.1	Summary of CTCAE Grade 3-4 Key Clinical Laboratory Values: Hematology	Safety Population	Y
LB_TAD	14.3.4.2.2	Summary of CTCAE Grade 3-4 Key Clinical Laboratory Values: Serum Chemistry	Safety Population	N
VS_TAA	14.3.5.1	Vital Signs Summary	Safety Population	Y
EG_TAA	14.3.5.2	12-Lead Electrocardiogram Summary	Safety Population	N
EG_TAB	14.3.5.3	Summary of Abnormal, Clinically Significant 12-Lead Electrocardiogram Values by Dosing Regimen and Visit	Safety Population	Y
EG_TAC	14.3.5.4	Summary of Clinically Notable 12-Lead Electrocardiogram Values by Dosing Regimen and Visit	Safety Population	Y

